## **2.0 Objectives**

### **Primary Objective**

To determine the feasibility of a clinical trial for omega-3 supplementation v. placebo in medical center team members for post-covid recovery.

This will serve as a proof-of-concept for a future, grant-funded study to evaluate the efficacy of omega-3 supplementation among a larger population recovering from covid-19.

### **Secondary Objective**

To determine which symptoms of long covid syndrome (if any) are most affected by taking an omega-3 supplement.

## **3.0 Background**

### **Supplement Interventions for Recovery of Post-Acute Sequelae of Covid-19 (Long Covid Syndrome)**

Since COVID-19 launched a worldwide pandemic in December 2019, non-prescription interventions have been and continue to be explored to limit the effects of the virus. As COVID-19 is novel, few studies on nutritional interventions have been completed. Much of the literature focuses on the breadth of possible or potential nutrition-based measures, including dietary protein, omega-3 fatty acids, vitamin A, vitamin D, vitamin E, vitamin B1, vitamin B6, vitamin B12, vitamin C, iron, zinc, and selenium [1]. Numerous analyses focus on Vitamin D, Vitamin C, and zinc [2,3,4]. Vit. D has been found to inhibit viral replication and have anti-inflammatory and immune-modulating effects, but as with other supplements used for prophylaxis, controlled trials specific to COVID-19 are needed [2, 4]. One longitudinal study in the UK, announced in June 2020, is examining Vit D status of 12,000 adults over the 2020-21 winter and will include a sub-analysis to determine if minority ethnic groups are more adversely affected [4]. Another study suggests that 2,000-5,000 IU of Vitamin D daily for older adults with Parkinson's disease (PD) may slow PD progression and have a protective effect against COVID-19 [5]. All of these studies, however, address active covid-19 infection, not the potentially long recovery period afterwards that is gaining worldwide attention.

The NIH has termed this symptomatic recovery period "Post-acute Sequelae of Covid-19" or "Long Covid Syndrome." To address this, NIH held its first workshop dedicated to the topic in December 2020 [6]. From severe hospitalized cases to mild outpatient cases, the road to recovery is complex and not yet well understood, though a few studies published thus far provide insights and researchers are beginning to study what interventions may be beneficial.

These patients, also known as long-haulers or those with post covid syndrome, have been shown to suffer from after-effects for 12+ weeks after contracting the virus. Effects may be most severe in patients with underlying lung disease such as asthma and/or who had a more severe form of covid-19, including those hospitalized. However, even

those having initially recovered from a mild case of the virus report long-term effects [7].

Long-term effects of covid-19 include loss of taste, loss of smell, continued need for oxygen therapy, and more. One New Jersey-based study on 183 patients from Hackensack University Medical Center found that at 35 days after discharge from the hospital following treatment for covid-19, 55% reported fatigue, 45.3% dyspnea, and 51% muscular pain, among other symptoms [8]. For some, post-covid syndrome lasts several weeks, while for others it may last several months. A small number of patients are thought to perhaps never return back to their pre-covid baseline.

According to the Mayo Clinic [7], the most common signs and symptoms of long covid syndrome are:

- Fatigue
- Shortness of breath
- Cough
- Joint pain
- Chest pain

Mayo Clinic states other long-term signs and symptoms may include: [7]

- Muscle pain or headache
- Fast or pounding heartbeat
- Loss of smell or taste
- Memory, concentration or sleep problems
- Rash or hair loss
- Organ damage, in particular:
  - “Heart. Imaging tests taken months after recovery from COVID-19 have shown lasting damage to the heart muscle, even in people who experienced only mild COVID-19 symptoms. This may increase the risk of heart failure or other heart complications in the future.
  - Lungs. The type of pneumonia often associated with COVID-19 can cause long-standing damage to the tiny air sacs (alveoli) in the lungs. The resulting scar tissue can lead to long-term breathing problems.
  - Brain. Even in young people, COVID-19 can cause strokes, seizures and Guillain-Barre syndrome — a condition that causes temporary paralysis. COVID-19 may also increase the risk of developing Parkinson's disease and Alzheimer's disease.” [7]
- Blood clots and blood vessel issues
  - “COVID-19 can make blood cells more likely to clump up and form clots. While large clots can cause heart attacks and strokes, much of the heart damage caused by COVID-19 is believed to stem from very small clots that block tiny blood vessels (capillaries) in the heart muscle.
  - Other parts of the body affected by blood clots include the lungs, legs, liver and kidneys. COVID-19 can also weaken blood vessels and cause

them to leak, which contributes to potentially long-lasting problems with the liver and kidneys.” [7]

- Mood and fatigue issues
  - “People who have severe symptoms of COVID-19 often have to be treated in a hospital's intensive care unit, with mechanical assistance such as ventilators to breathe. Simply surviving this experience can make a person more likely to later develop post-traumatic stress syndrome, depression and anxiety.
  - Because it's difficult to predict long-term outcomes from the new COVID-19 virus, scientists are looking at the long-term effects seen in related viruses, such as the virus that causes severe acute respiratory syndrome (SARS).
  - Many people who have recovered from SARS have gone on to develop chronic fatigue syndrome, a complex disorder characterized by extreme fatigue that worsens with physical or mental activity, but doesn't improve with rest. The same may be true for people who have had COVID-19.” [7]

It must be noted that other long-term health effects of covid-19 are continually being discovered, so the list of symptoms may change over time. A UK study of 100 patients who recovered from covid-19 found that 4-8 weeks after hospital discharge, 72% of those who had been in the ICU reported ongoing fatigue, breathlessness (65.6%), psychological distress (46.9%) and a 68.8% drop in EQ5D (quality of life). For those not in the ICU, 60.3% reported continued fatigue, breathlessness (42.6%), psychological distress (23.5%) and a 45.6% reduction in EQ5D [9]. A study in France of 120 patients hospitalized for covid and studied approximately 110 days after admission, found that the “most frequently reported persistent symptoms were fatigue (55%), dyspnoea (42%), loss of memory (34%), concentration and sleep disorders (28% and 30.8%, respectively)” [10]. There were no statistically significant differences between ICU and non-ICU patients. Measures of mobility, self-care, pain, anxiety or depression and usual activity were also similar, except for a “slight difference in pain in the ICU group” [10].

Even in younger (age 18-34) patients who were never hospitalized, a CDC phone survey found 1 in 5 were not back to their previous healthy state 14-21 days after testing positive [11].

Inflammation may be a common thread with multiple effects from long covid syndrome. A common complaint is “brain fog” or challenges with thinking clearly, which may be related to post-covid fatigue linked to ongoing inflammation [12]. Physicians report ongoing inflammation of the brain and nervous system, resulting in a cascade of effects including toxicity and dysregulation [13]. One of the more prevalent effects is seen in a study reported in JAMA Cardiology. It found 78 of 100 recently recovered covid patients in Germany had cardiac issues as seen on cardiovascular magnetic resonance (CMR) imaging, while 60 had ongoing myocardial inflammation [14].

One of the challenges with long covid syndrome is that the length of time it lasts is not

yet known, and could span from weeks to years [12]. A study of 143 patients in Rome, Italy who had been hospitalized with covid and recovered, found that 87.4% had at least one persistent symptom [15]. In particular, 53.1% still reported fatigue, 43.4% had dyspnea (breathing difficulties), 27.3% reported joint pain, and 21.7% had chest pain [15].

The Rome-based study team, located at the Fondazione Policlinico Universitario A. Gemelli IRCCS, asserts that geriatricians are best able to manage the multidisciplinary needs of post-covid patients: “In fact, the geriatrician is the specialist who best can manage the multidimensional health problems, with a great aptitude and skill to cope multimorbid and complex patients. Second, geriatricians are the doctors who best know the principles of teamwork in close collaboration with the other health care professionals and family. In particular, the geriatrician is able to manage the onset of the most important syndromes, such as sarcopenia, malnutrition, depression, and delirium.” [16]

The study outlined in this protocol is managed by a geriatric team from the Center for Healthy Senior Living (CHSL) at Hackensack University Medical Center in Hackensack, New Jersey.

### **Omega-3 Supplementation**

The Covid-19 infection is characterized by a very strong inflammatory response of the body and often results in a “Covid-19 pneumonia”, similar to what is known as Acute Respiratory Distress Syndrome (ARDS). Pharmacotherapies that moderate inflammation in ARDS/Covid-19 pneumonia are lacking.

It is known that Covid-19 infection can cause severe pneumonia inflammation, triggering a pro-inflammatory “cytokine storm” expressed through a high expression of IL-6 and tumor necrosis factor (TNF), subsequent release of pro-inflammatory prostaglandin E2 (PG), 5-lipoxygenase (LOX) and leukotrienes. High levels of free nitric oxide (NO)-radicals causing oxidative stress and damage to the cell tissue. Additionally, at the late stage of the disease, neo angiogenesis has been seen to be a crucial step of lung fibrosis, leading finally to a fatal ARDS condition.

The effects of omega-3 fatty acids, in particular EPA, on the many different inflammatory pathways have been well studied and described in the literature [17]. Many of these papers discuss the anti-inflammatory effects of the omega-3 fatty acids in relation to cancer development and treatment [17] and inflammatory bowel disease such as ulcerative colitis. Although these inflammatory disorders have nothing to do with Covid-19, the basic principle of inflammatory response and anti-inflammatory pathways within our body cells is highly likely to be the same, whether we focus on ulcerative colitis, colon cancer, rheumatoid arthritis or “Covid-19 pneumonia”.

It is well known that the pro-inflammatory eicosanoids are derived from a polyunsaturated omega-6 fatty acid called Arachidonic Acid (AA) through the

cyclooxygenase (COX-), LOX- and p450 epoxygenase pathway. These pro-inflammatory eicosanoids:

- increase the vascular permeability
- promote platelet aggregation
- recruit neutrophils
- cause edema
- release pro-inflammatory substrates such as cytokines which in turn lead to the production of chronic inflammatory mediators like IL-1 $\beta$ , IL-6, IL-8 and TNF $\alpha$

The same COX and LOX enzyme-systems are responsible for converting the omega-6 arachidonic acid into pro-inflammatory eicosanoids or alternatively the omega-3 EPA into anti-inflammatory eicosanoids. Thus, there is a strong competitive interaction between the AA and EPA with COX- or LOX enzyme systems in the body cells. If the concentration of AA is dominant, then more pro-inflammatory eicosanoids are generated. However, if there is more EPA present, then more anti-inflammatory eicosanoids are produced and the intensity of an inflammatory attack is reduced. Both AA and EPA originate from our diet. A diet rich in red meat, milk, milk products, cheese and eggs combined with the use of omega-6 rich vegetable oils like sunflower or corn oil will result in a high concentration of pro-inflammatory arachidonic acid in the cell membranes. A diet rich in fatty fish (sardines, anchovy, salmon, mackerel, tuna) in combination with neutral vegetable oils like olive oil will result in a more equilibrated ratio of omega-6 to omega-3 in the cell membranes. EPA partly displaces AA in our cell membranes [18,19] and reduces the formation of pro-inflammatory cytokines [20].

### Rationale

Marine derived omega-3 polyunsaturated fatty acids (PUFA) supplementation have been shown to have a significant lowering effect on C-reactive protein, IL-6 and TNF which slows down the AA cleavage from the cell membrane and subsequent synthesis of COX/LOX generated pro-inflammatory eicosanoids [21]. Furthermore, by downregulating the NF $\kappa$ B with help of the EPA dependent IKK $\beta$ -complex not only less IL-6 is expressed but also less vascular endothelial growth factor (VEGF), which in turns reduces the neo angiogenesis activity, a suppression highly desired during the Covid-19 pneumonia infection, and which may be beneficial in reducing ongoing symptoms of post-covid syndrome.

Nitric oxide (NO), a free radical derived from L-arginine by nitric-oxide-synthase (NOS) is proposed to play an important role in many inflammation processes and leads to severe inflammation related tissue damage. The oxidative stress triggered by NO may also additionally activate NF $\kappa$ B [22] and in turn increase further the “inflammatory storm”. Omega-3 fatty acids, in particular EPA, is involved in several different metabolic pathways which down-regulate the NOS gene expression, resulting in a decreased NO production thus tissue damage [23]. Another important point of inflammatory down-regulation by EPA is competitive regulation of the COX-2 system. If the cell membrane contains a high content of EPA, then the probability that an EPA molecule connects with

the COX-2 system and generates anti-inflammatory eicosanoids is much higher than in the case that the pro-inflammatory AA dominates in the cell membrane [24].

Additionally, EPA is converted in the body to very potent pro-resolving mediators (PRMs) known as resolvins, protectins and maresins. These very active compounds reduce the magnitude and duration of inflammation, stimulate wound healing and regenerate damaged tissue.

ARDS and ICU studies [25, 26, 27] of immunonutrition with omega-3 (enteral supplementation) after the start of hospitalization showed positive results within two weeks. A significant reduction in pro-inflammatory eicosanoids was evident after 24 hours [25]. In this study, the patients received during a period of 12 hours an enteral nutritional supplement containing 10% fish oil. The administered dose was 0.12g/kg/h. Taking into consideration an average body weight of 75kg, the patients would have received, within the 12-hour supplementation period, a total of approximately 3 g Omega-3 of which roughly 2 g would have been EPA in the natural triglyceride form. Numerous other studies discussed in [26, 27, 28] also indicated clear benefits of an Omega-3/fish oil treatment for hospitalized ARDS patients, including a reduced mortality. The effects on long-term symptoms from covid-19 are just beginning to be explored among researchers, making this study among the first.

### **Considerations for COVID-19 among Healthcare Workers in New Jersey**

As the densest state in America, New Jersey has been particularly hard-hit by coronavirus cases [29]. With 516,608 confirmed cases statewide as of January 8, 2021, those over age 65 have been greatly affected, comprising 16.8% of cases [30] and 79.8% of the state's 17,587 lab-confirmed deaths as of January 7, 2021 [30].

Healthcare workers – the subject of this study – have also been devastated by the virus. A study of NJ healthcare workers (HCW) early in the pandemic found that these employees were at greater risk for becoming infected than non-healthcare workers [31]. A 7.3% prevalence of infection was found among NJ healthcare workers versus 0.4% among non-healthcare workers [31]. Infections were particularly high among Black, Latino and “other” races [31]. The study acknowledged that further research is needed “to examine whether racial differences in COVID-19 among HCW may be related to their particular roles in the health care setting or are reflective of residence in communities that are more vulnerable to infection.”[31] More recent news attests to NJ team members continuing to fall ill, including over 100 at Hackensack Meridian Ocean Medical Center in December 2020 [32]. Statistical analysis in our study will examine demographic information such as race and occupational role.

## **4.0 Study Endpoints**

### **4.1 Primary Outcome Variables**

The primary endpoint is evaluation of feasibility and acceptability of omega-3

supplementation v. placebo to limit post-covid syndrome among adult patients. The Follow-up Feasibility Survey (Appendix D) will be used for this analysis.

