## 1.0 Study Summary

Study Title	HMH Omega-3 Covid Recovery Study
Study Design	We will conduct a two-arm, double blind randomized 12-week study to supplement omega-3 (EPA + DHA) among 100 adults (age 18+) who had covid-19 and are experiencing possible after-effects from the illness (post-acute sequelae of covid-19, also called post-covid syndrome or long covid syndrome).
Primary Objective	The primary objective is to serve as a feasibility study for omega-3 fatty acid supplementation v. placebo in adult patients to limit long covid syndrome. This will serve as a proof-of-concept for a larger follow-up study to subsequently be conducted.
Secondary Objective(s)	Determine which of the post-covid symptom(s) are most impacted by omega-3 supplement.
Research Intervention(s)/Investigational Agent(s)	Participants will be assigned to one of two study arms and asked to take an Omega-3 supplement or placebo for 12 weeks. Participants will report symptoms bi-weekly throughout the study period. A spot blood sample to assess omega-3 levels will be done at baseline and at the end of the 12-week study period.  A survey will be used bi-weekly to assess health status and outcomes via patient self-report. Data on demographics and comorbidities such as obesity and diabetes will be collected at baseline. At the end of study participation, subjects will take a follow-up survey assessing feasibility.
IND/IDE #	IND # 157250
Study Population	Hackensack Meridian Health team members age 18+ who tested positive for COVID-19 28+ days prior and who are not already taking an Omega-3 supplement.
Sample Size	50 participants in each arm = 100 total for final analysis (up to 60 participants in each arm will be recruited if needed, dependent on attrition for a total of up to 120)
Study Duration for individual participants	Individual participants will be in the study for 12 weeks. During the 12 week study period, subjects will be sent a survey every two weeks. At the end of the 12 weeks, subjects will complete a short survey collecting feasibility and acceptability data.
Study Specific Abbreviations/Definitions	
 
• Hackensack Meridian Health (HMH)
 
• Center for Healthy Senior Living (CHSL)
 

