## 9.0 Study Timelines

Each subject will spend 12 weeks in the study.

It is anticipated that all subjects will be enrolled within a 6-month timeframe.

	Month 1	Month 2	Month 3	Month 4	Month 5	Month 6	Month 7	Month 8	Month 9	Month 10	Month 11	Month 12
IRB approvals & startup	X	X	X									
Enrollment				X	X	X	X	X				
Subjects on study (12 weeks)				X	X	X	X	X	X	X	X	X
Interim analysis at 3 weeks					X							
Final data analysis										X	X	X

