## **12.0 Local Number of Subjects**

The number of subjects will be 50 in each of two arms, for a total of 100 subjects for analysis. Up to 60 participants in each arm will be recruited if needed, dependent on attrition, for a total of up to 120 subjects.

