## Follow-up Survey - Covid Recovery Study

Please complete the survey below.

Thank you!

Were the instructions on how to take the pills clear?

Yes  
 No  
 Neutral / I don't know

If no, why not?

Did you not take the pills (skip one or more doses) at any time during 12-week study? (please refer to your pill log calendar)

No  
 Yes

If yes, how often did you not take the pills?

For how many days in a typical week did you take the pills?

Please include any comments about missed doses here:

Were the pills easy to take?

Yes  
 No  
 Neutral / I don't know

If no, why not?

Did taking the pills interfere with your daily activities somehow?

Yes  
 No  
 Neutral / I don't know

If yes, how?

How satisfied were you with your experience taking the pills?

Very satisfied  
 Satisfied  
 Neutral  
 Dissatisfied  
 Very dissatisfied

Are you willing to be contacted in the future about opportunities to participate in other research studies?

Yes  
 No

Confidential

Page 2

Since starting your participation in this study, has any doctor or other health care provider told you that you have any of the following illnesses? (please check all that apply)

- Diabetes or high blood sugar
- Hypertension or high blood pressure
- High cholesterol
- Stroke (ischemic or hemorrhage)
- Chronic lung disease such as asthma, emphysema, or chronic bronchitis
- Heart disease
- Cancer (other than skin cancer)
- Depression
- HIV/AIDS
- Other

If you answered "Other," please specify:

---

Please share anything else you would like us to know about your experience participating in this study:

---

During the 12-week study, did you receive the covid-19 vaccine?

Yes  
 No

If you did receive the covid-19 vaccine, did you experience any side effect(s)?

---

For how long did you experience side effect(s)? (please specify in # of days)

---

Is there anything else you would like to tell us that you might be important that we did not ask about?

---

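### The primary feasibility endpoint rests on a week-12 survey about taking pills, while the stated objective is the feasibility of a trial; no recruitment, retention or procedure-completion measure belongs to any endpoint

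*Combined protocol and SAP*

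**What the plan says.** Section 2.0 gives the primary objective as "To determine the feasibility of a clinical trial for omega-3 supplementation v. placebo in medical center team members for post-covid recovery", and adds its purpose: "This will serve as a proof-of-concept for a future, grant-funded study to evaluate the efficacy of omega-3 supplementation among a larger population recovering from covid-19".

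Section 4.1 defines the primary endpoint as feasibility and acceptability of the supplementation and names one source: "The Follow-up Feasibility Survey (Appendix D) will be used for this analysis". Section 1.0 places that survey in time: "At the end of the 12 weeks, subjects will complete a short survey collecting feasibility and acceptability data". Section 6.2 likewise lists it in the final study activity.

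The survey in Appendix D asks, for example, "For how many days in a typical week did you take the pills" and "How satisfied were you with your experience taking the pills". Appendix D also holds a short discontinuation form, and section 6.2 requires a dedicated REDCap form for anyone who stops, whether removed for non-compliance or by choice.

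On recruitment and attrition the plan makes planning statements only. Section 9.0: "It is anticipated that all subjects will be enrolled within a 6-month timeframe". Section 12.0: "Up to 60 participants in each arm will be recruited if needed, dependent on attrition, for a total of up to 120 subjects".

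Section 17.1 says that all study data will be summarised descriptively, overall and by arm. It then labels a chi-square or Fisher comparison of symptom recovery the primary analysis.

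**The concern.** A feasibility trial that is meant to prepare a larger one has to say whether people can be recruited, kept and taken through the procedures. Here the only instrument named for the primary endpoint asks about something narrower, and asks it of a selected group.

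At stake is what the headline result means. Slow enrolment, heavy loss or poorly completed surveys and blood spots would not appear in the primary endpoint as written. They could be described afterwards, but what counts as feasible would then be chosen with the results in view. The label in section 17.1 adds to this: a reader who looks for the primary analysis finds an efficacy comparison that matches neither the objective in section 2.0 nor the endpoint in section 4.1.

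**Working it through.** **1. The four statements of what is primary.**

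| Place | What is primary |
|---|---|
| 1.0 Study Summary | Feasibility study of supplementation against placebo |
| 2.0 Objectives | Feasibility of a clinical trial |
| 4.1 | Feasibility and acceptability of supplementation, from the Appendix D survey |
| 17.1 | Between-arm test of symptom recovery |

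The first and third agree with each other. The second is wider, and the fourth is a different question.

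**2. What the survey covers.** Its structured feasibility items are clarity of the pill instructions, skipped doses, days of pill-taking per week, ease, interference with daily activities, and satisfaction with the pills. The other items are willingness to be re-contacted, new diagnoses, vaccination and free text. No structured item covers the home blood spot, the bi-weekly surveys, self-measured blood pressure, the weekly calls or placebo allocation. Experience of these can surface only in free text.

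**3. Who answers it.** The survey comes at the end of week 12. Subjects with repeated missed doses under the rule in sections 6.2 and 14.0 are removed earlier and directed to the discontinuation form. That form asks three things: whether participation has stopped, how many pills remain, and whether they were discarded. The least adherent subjects can therefore leave before the adherence and satisfaction questions are put to them.

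An illustration of the effect, assuming 120 randomised (the cap in section 12.0), r completers who all answer, and 90% of them satisfied. Survey result = 0.9r/r; retention = r/120; satisfied among all randomised = 0.9r/120.

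| Completers r | Satisfied | Survey reads | Retention | Satisfied / 120 |
|---|---|---|---|---|
| 60 | 54 | 90% | 50% | 45% |
| 80 | 72 | 90% | 67% | 60% |
| 100 | 90 | 90% | 83% | 75% |
| 120 | 108 | 90% | 100% | 90% |

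The survey result is the same in every row.

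**4. The plan's own figures.** The sample size of 100, with a cap of 120, cannot be reproduced: no power, effect size, attrition rate, threshold or target precision is given. The step from 100 to 120 implies attrition of 1 − 100/120 = 16.7%, or 20/100 = 20% if the extra is taken as a share of 100. Six months of enrolment implies 100/6 = 16.7 to 120/6 = 20 subjects per month. The timeline table in section 9.0 marks only five enrolment months, which implies 100/5 = 20 to 120/5 = 24.

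**5. Whether this trial can estimate retention.** It can. For 100 of 120, p = 0.833, and the Wilson 95% interval is [p + z²/2n ± z√(p(1−p)/n + z²/4n²)] / (1 + z²/n). With z = 1.96 and n = 120 this is (0.8493 ± 0.0686)/1.0320, or 75.7% to 88.9%. Per arm, 50 of 60 gives 72.0% to 90.7%.

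**6. What any progression mark must satisfy.** To have 100 analysable from E enrolled, retention must be at least 100/E: 100% at E = 100, 90.9% at E = 110, 83.3% at E = 120. A pair of marks such as 100 enrolled and 83% retained would leave about 100 × 0.833 = 83 analysable, short of the planned 100. At exactly 100/120 the estimate meets 83.3%, but the lower confidence limit is 75.7%, so a rule has to say which of the two must pass.

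**The case against.** The best defence is that sections 1.0 and 4.1 speak of the feasibility of supplementation, for which a survey of adherence and pill acceptability is a reasonable instrument. On that reading the fault lies in the wording of section 2.0. This has weight, and it is why the sections should be reconciled and not only section 4.1 changed. It does not remove the problem: section 2.0 still states the wider objective, and even feasibility of supplementation is poorly shown by a survey scheduled only for those who reach week 12.

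Second, a reader might infer that attrition goes unmeasured, or that the trial is incapable of showing feasibility. The documents do not support that. Discontinuation is recorded, section 17.1 promises summaries of all data, and enrolment, survey and laboratory results will exist. Whether the reference to Appendix D in section 4.1 takes in the discontinuation form is arguable, but the survey is what it names. Even if the form is included, no retention measure is defined from it. The gap is one of pre-specification and denominator, not of absent data.

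Third, willingness to do the surveys, the blood pressure readings and the blood spots, and to accept either arm, is already asked in Appendix A (items 12 to 14 and 17). Those who decline become ineligible, so a consent rate among eligible people alone would hide them.

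Finally, which feasibility measures to promote is partly a matter of judgement. That stands; the list under the fix is one sound choice.

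**Conclusion.** The point holds as a mismatch between objective, endpoint and primary analysis. The named instrument answers a narrower question than section 2.0 asks, is selective for completers, and leaves recruitment, retention and procedure completion outside every endpoint. It should be corrected, although the trial can run without the change.

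The 50% to 100% span of retention behind one survey result is an illustration that rests on the assumed 90% satisfaction and 120 randomised; it is not a forecast.

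Three stronger inferences should not be drawn. The plan would not declare the trial feasible despite poor conduct, because it contains no success criterion at all. Section 16.0 mentions deciding whether a larger study is warranted, but as a benefit to society and not as a decision rule. And 83% retention or 100 enrolled in six months are not protocol targets: 120 is a ceiling, no attrition rate is stated, and the six months is an expectation.

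**What to change.** Reconcile sections 1.0, 2.0, 4.1 and 17.1 so that feasibility is both the primary objective and the primary analysis, with symptom recovery as secondary.

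Define the primary feasibility endpoint in section 4.1 from trial records, each measure with a 95% CI and, for everything after randomisation, with all randomised subjects as the denominator:

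- subjects enrolled per month;
- consented among those screened and among those eligible, with counts of those declining at Appendix A items 12 to 14 and 17;
- retention at week 12;
- proportion of bi-weekly surveys completed (12/2 = 6 per subject);
- paired blood-spot results received from the laboratory, since subjects mail the samples there directly;
- adherence, including those who discontinue.

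Keep the Appendix D survey as the acceptability component, optionally with one item each on the blood-spot kit, the surveys, blood pressure and the calls.

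If progression marks are wanted, the sponsor should choose them in advance, state whether the estimate or the confidence limit must meet them, and make them jointly consistent with 100 analysable from at most 120 recruited.

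The cost is amendment wording and at most about four survey items, with no new visit or procedure. The small downside is that the feasibility result can then come out unfavourable.
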